**POTENTIAL BENEFITS:**

The purpose of this study is to evaluate whether participants with NF1 will benefit from improved thinking/learning, behavior, and movement in response to eight (8) weeks of treatment with N-Acetylcysteine (NAC). There is a potential for direct benefit by participating in this study if the treatment improves the symptoms of motor behaviors and learning associated with NF1. However, there is a possibility of no direct benefit to the participant.

In addition to possible benefits of the study drug, medical records and/or study assessments will be reviewed by our multidisciplinary team that includes geneticists, neurologists, neuropsychologists, and radiologists. Any findings that may possibly impact the participant's health and well-being will be reviewed with the parent/caregiver and appropriate referrals for further testing or management will be made by a physician on the study team. Returned results will be based solely on the baseline assessment, when the most complete information is available, and when any practice effects have not yet occurred that could distort norm-referenced interpretations. This will be of use to help tailor other interventions to individual participants.

When we finish the research, we expect that we will know more about NF1 and the associated cognitive (thinking) and motor (movement) concerns. This may help participants in this study as well as other children with NF1.

**POTENTIAL RISKS, DISCOMFORTS, INCONVENIENCES AND PRECAUTIONS:**

**Known and potential discomforts or hazards of single and paired pulse TMS:**

Single and paired pulse TMS has been used at CCHMC under [name] direction since 2001 for research only. Potential discomforts are mild and transient. In a prior study of 40 healthy and ADHD children, Garvey et al asked children to rank TMS compared to other childhood activities. TMS was ranked preferable to 1) a "shot"; 2) going to the dentist; and 3) a long car ride. The following mild, transient effects were reported in our prior study of 35 children and adults: scalp discomfort (12%), hand weakness (9%), headache, neck pain, arm pain, and arm tingling (6%), hand pain, decreased hand dexterity, hearing changes, and tiredness (3%). All of these had resolved by the following day. There were no physical findings after TMS supporting the subjective descriptions of loss of strength or dexterity. A prior common concern about use of TMS was the risk of seizures [28]. We follow recommended guidelines [28] and have seen no seizures in children or adults studied at our center. In addition, more recent studies even in children with epilepsy suggest that the risk of TMS inducing seizures is extremely low.

**Known and potential discomforts or hazards of MRI/MRS:**

There are no known risks injury associated with a brain MRI/MRS. A few common less serious risks have been reported and are described here. Participants susceptible to claustrophobia may experience anxiety during the scan. The noise generated by the MRI/MRS machine can be

uncomfortable for some participants. Ear protection will be available to minimize the noise exposure. Participants may experience mild muscle/nerve stimulation that may feel like a twitching sensation.

Participants with a medical implant or external accessory device may experience complications with that device while undergoing an MRI/MRS. One potential complication is that the device may move in response to the magnet. Implants, external and accessory devices may heat up in response to the magnet, which could lead to burns. A third potential complication is the potential that electrochromic implants, external and accessory devices may malfunction in response to the magnet. To mitigate the risk of harm, we have included the use of such implants/devices as an exclusion factor for this study.

#### **Known and potential discomforts or hazards of NAC**

NAC is FDA approved for treatment of acetaminophen overdose, respiratory disease due to mucous obstruction in acute and chronic settings in children and adolescent. Common side effects include pruritus, rash, urticaria, diarrhea, nausea, and vomiting. NAC may not be effective for every participant, therefore participants may experience a continuance or worsening of their condition, including school performance or social interaction, while in the study.

#### **Precautions, risk minimization:**

The protocols include a number of precautions to minimize risk. Standard of care will be followed for all procedures performed to decrease the risk of infection, pain, bleeding, and bruising. The TMS laboratory was established in 2001 in consultation with [name], an internationally known researcher in transcranial magnetic stimulation. A trained and TMS-administration certified neurologist will be present during TMS. All subjects will wear 34 NRR earplugs or headphones during TMS if the head is stimulated at an intensity of over 90%. Standard exclusion criteria are applied for participation in this study. Detailed questioning for any adverse events will occur after the experiment and the next day after the study. Access to the Magstim Stimulator is Limited – these TMS devices are kept in room 4 of the EEG lab on the seventh floor of the A tower. The laboratory is continually monitored by CCHMC during business hours and is locked at all other times.

The effects the study drug and procedures would have on a fetus are unknown. When deemed appropriate by the study doctor or designee, pregnancy testing will be utilized before study procedures will take place. Females that test positive for pregnancy will be excluded or withdrawn from the study. Risks to a fetus conceived while on study drug will be reviewed with all parents. A conversation about risks and the importance of contraception while in this study will also be conducted with participants when deemed appropriate by the study doctor or designee. Consent to participate in this study includes promise of compliance with appropriate contraceptive measures. Females will use an effective means of birth control (i.e. abstinence, hormonal, or intrauterine device) during the study and for 30 days after taking the last dose of study drug. Males will use an effective means of birth control (i.e. abstinence or double-barrier contraception) during the study and for 90 days (3 months) after taking the last dose of study drug.

#### **The method of monitoring study conduct:**

Adverse events will be reviewed using direct questions with a detailed review of systems on the day of the study. The principal investigator or designee is responsible for reporting adverse events to Cincinnati Children's Hospital Medical Center Institutional Review Board. Unanticipated events will be reported to both IRBs, according to the individual IRBs' requirements.

DoD representatives can independently review and inspect research associated with this study. They can prohibit research that is determined to present unacceptable hazards or is non-compliant with DoD regulatory requirements.

**Methods for maintaining data quality and confidentiality:**

Data are maintained in case report folders identified only by an anonymous subject ID. They will be kept in a secured area of Cincinnati Children's Hospital. All data kept in computerized files are in computers or a server with restricted, password-protected access. Only the primary investigator and designated study staff within his laboratory have access to case report folders and computer passwords (restricted by access level). A participant will be identified throughout the central database by his or her unique subject identification number (SID). Information which could identify a subject, such as name, address or social security number, will either not be stored electronically. A database audit trail of all data element changes over the life of the study will be maintained.

Data will be kept in a separate data base without demographic and clinical information and will be merged during the analytic stage of the study. Data entry, verification and validation will be carried out using our proprietary clinical data management system. We have a fire-wall-protected and local-network-based database management system for paper-based data collection, reports processing and information handling.

The study PI is responsible for overseeing execution of the research. Oversight responsibilities apply to all human subjects' research, whether or not it is determined to be exempt from the regulations.

**RISK/BENEFIT ANALYSIS:**

In the opinion of the investigative team, this study, based on our experience with NAC and with administering TMS as well as the published literature on NAC and TMS, involves minimal risk, with potential for direct benefit.

**DATA SAFETY AND MONITORING:**

Data Safety Monitoring Plan:

Steps to be taken to assure the accuracy of the study data: The study team will review case report forms, source data, and spreadsheet entries once annually to ensure accuracy of data entry.

Adverse events and unanticipated events will be classified based on severity and attributed to individual components of study participation. For example, if a subject reports nausea at the end of the TMS baseline visit, this will be classified based on severity rating from the subject (mild, moderate, severe in the case report forms) and relationship to study tasks will be ascertained as well as possible (related to TMS, related to study medication, related to both, related to neither, unsure) on a case report form.

An external safety monitor will not be utilized for this minimal risk study. The study is deemed minimal risk because of the unrestricted availability of the study drug.

**PRIVACY AND CONFIDENTIALITY:**

Privacy of the individuals participating in this proposed study will be maintained through non-identifying subject ID codes (SID), locked storage and password protected files. External collaborators will have access to de-identified research records only. Distribution of participant medical records to external collaborators will be done via secure email transmissions. The study log will be maintained in a password protected folder on the desktop computer of the principal investigator. Case reports and spreadsheets will refer to subjects by number only. Subjects will be informed that, if necessary, the IRB or FDA may review the data.

DoD representatives will be allowed to independently review and inspect the awardee's research. This may include access to identifiable information or protected health information. Participants will be informed about this risk to confidentiality.

**COST OF PARTICIPATION:**

There will be no charges to participants or to third party payers related to study visits or procedures in this study. NAC is an FDA approved medication. NAC will be provided for the 8 week duration of the study to all participants.

**COMPENSATION/PAYMENT FOR PARTICIPATION:**

Families will be compensated for time, effort, and travel as described in the table below. For the first 3 study visits, each participant will receive \$25. Study visit 4 has additional conditions (i.e.: return of drug diary and unused drug), therefore, each participant will receive \$100 for that visit. Total compensation for this study per participant is \$175. Reimbursement will be distributed within 90 days of study completion or withdrawal.

Payment Schedule			
Visit 1 $\psi$	Visit 2	Visit 3	Visit 4
\$25	\$25	\$25	\$100

$\psi$  Indicates treatment- and non-treatment cohort payment

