### **STUDY DESIGN:**

This is a prospective single-center; randomized, double-blind, placebo-controlled Phase II study to determine the safety and efficacy of NAC on motor behavior and/or attention deficits of children with NF1 aged 8 to 16 years. Participants will be randomized to 8-weeks of treatment with NAC (70 mg/kg/day) versus placebo. This is a collaborative study between multiple specialties at CCHMC and external collaborators at Children’s National Hospital and Technion Israel Institute of Technology. We have received IND approval from the FDA to use NAC for the application in this study (IND# 139468).

It is plausible and ethical to employ a placebo group, as no standard therapy with established efficacy is being withheld. There is no crossover in this study due to a lack of data concerning the length of possible washout effects. Primary and secondary outcome measures will be administered at baseline, after 8 weeks of treatment and at follow-up, 4 weeks after cessation of treatment to determine any washout effects.

In addition, the effect of NAC on measures of impulsivity, attention, executive function, and SICI and imaging biomarkers will be assessed. Participants will be carefully monitored for side effects by a medical safety monitor for the study. The safety of NAC will be evaluated using laboratory tests, clinical signs and adverse effects, which will be monitored at regular intervals over the 8-week treatment period.

An additional cohort of age/sex-matched NF1 participants will be recruited in order to characterize and validate biomarkers of brain function.

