## **STUDY PROCEDURES:**

### **Study Variables and Measurements - Overview:**

We propose to study all measurements at baseline, 8 weeks after treatment, and 4-week post-treatment (washout period) to assess for carry-over effects. We will compare PANESS and SICI measures in 58 children with NF1 to data already acquired at CCHMC for those 2 measures (**Figure 14**). Next, these children will be treated with NAC (n=29) or placebo (n=29) as described above (**Figure 16**).

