**Table 4: Schedule of Assessments**

	Visit 1	Visit 2				Visit 3		Visit 4
	Screening	Baseline	Abbreviated Remote monitor and safety	Remote monitor and safety	Abbreviated Remote monitor and safety	End Intervention	Remote monitor and safety	Follow Up
Task	Week 0	Week 1	Week 2	Week 4	Week 6	Week 8	Week 10	Week 12
Review Eligibility Criteria $\Psi$	X							
KBIT-2 (Kaufman Brief Intelligence Test, Second Edition) $\Psi$	X							
KSADS (MedHis)	X							
Cognitive Function Screening $\Psi$	X							
Test dose	X							
Informed Consent $\Psi$	X							
Brain Imaging (MRI/MRS) $\Psi$		X				X		X
Urine Pregnancy (Females only)	X	X						
Vitals*		X				X		X
Safety labs*		X				X		X
Physical Exam*		X				X		X
ADHD-RS (DuPaul) $\Psi$		X		X		X	X	X
KSADS (CC)		X		X		X	X	X
PARS (Pediatric anxiety rating scale)		X		X		X	X	X
CDRS (Children's depression rating scale)	X	X		X		X	X	X
C-SSRS (Columbia Suicide Severity Rating Scale)	X	X		X		X	X	X
Wechsler Intelligence Scale for Children, Fifth Edition (WISC-V) $\Psi$	X	X				X		X
Behavioral Rating Inventory of Executive Function (BRIEF-2) $\Psi$		X				X		X
Test of Variables of Attention (TOVA) $\Psi$		X				X		X
PANESS scale $\Psi$		X				X		X
TMS assessment $\Psi$		X				X		X
NAC/Placebo Prescription		X						
Med Log		X	X	X	X	X	X	X
AE assessment (MedDRA)		X	X	X	X	X	X	X
Follow-up plan								X

\* Indicates clinical procedures performed as standard of care

$\Psi$  Indicates research procedures to be completed in both treatment and non-treatment cohorts

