**COMPLIANCE AND SAFETY MONITORING:**

Monitoring and Managing Adherence to Treatment:

Pill/Sachet counts and/or review of the medication log will be used to estimate compliance, along with queries about missed doses. We will require a standard of four days out of seven on treatment to obtain a rating but will counsel the participant and family about the importance of adherence in such a situation. We will require a minimum of 5 days per week on treatment in each of the final two weeks of each treatment block, so that the end-of-treatment ratings are an accurate reflection of treatment. For the final study visit and pTMS assessment, subjects must have 100% compliance for the two days prior to testing or testing will be rescheduled within a reasonable 3-4 day window so that compliance can be assured.

Communication:

To facilitate data collection, safety monitoring, and accommodate preferences of participants, communication between study staff and the research participant/family/teachers will utilize a variety of technologies. Modes of communication may include phone calls, videoconference, electronic mail (e-mail), REDCap surveys (via e-mail link or Twilio text message), and in person meetings. Responses to safety assessments will be reviewed by a member of the study team within 48 hours. As described elsewhere, if a participant/family discloses any suicide ideation or significant health concerns at any point in this study, the study staff will contact the participant's mental health provider or primary care provider and/or Psychiatric Intake Response Center (PIRC) at CCHMC for further assessment and guidance within 24 hours.

Video recordings may aide recruitment and explanation of study assessments/details. These recordings may be distributed in a similar manner to other advertisements (websites, philanthropic/educational events, through interactions related to clinic visits, distributed via REDCap correspondence, et cetera). Examples or video content would be a short description of TMS and PANESS procedures. A general outline of the study (risks/benefits, procedures, timeline, et cetera) as would be described during informed consent would also be advantageous.

Medical/safety assessments:

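### Return of unused study drug is timed to Visit 4, after the washout, and no drug return or count is assigned to Visit 3

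*Combined protocol and SAP*

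**What the plan says.** The section on compensation pays $25 for each of the first three visits and $100 for the fourth. It explains the larger sum as follows: "Study visit 4 has additional conditions (i.e.: return of drug diary and unused drug". This is the only place in the combined protocol and SAP that times the return of drug or diary.

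The Study Design section places the last assessment "at follow-up, 4 weeks after cessation of treatment to determine any washout effects". The overview of study variables gives the same purpose: "4-week post-treatment (washout period) to assess for carry-over effects".

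Table 4 marks "NAC/Placebo Prescription" once, at Visit 2. It labels Visit 3 (Week 8) as the end of the intervention and Visit 4 (Week 12) as follow-up. A medication log is scheduled at every contact from baseline to Week 12. No visit has a row for drug return or drug count.

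On supply, the Cost of Participation section says "NAC will be provided for the 8 week duration of the study to all participants". The quantity handed out is not stated.

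On adherence, the Compliance and Safety Monitoring section says "Pill/Sachet counts and/or review of the medication log will be used to estimate compliance, along with queries about missed doses". It sets a general floor ("We will require a standard of four days out of seven on treatment to obtain a rating") and a higher one of five days per week in each of the last two treatment weeks. It names no visit for the counts.

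**The concern.** Two uses of the returned drug are weakened by its timing.

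The first is the washout reading. Week 12 can show what remains of an effect after NAC stops only if the preceding four weeks are free of NAC. Under the stated timing, the drug is handed in when that interval is already over. Continued placebo should do nothing, whereas continued NAC could sustain an effect. Any use of leftovers would therefore tend to make NAC look more persistent than it is. The Study Design section gives the lack of data on the length of washout effects as the reason for not using a crossover, so this is information the trial is well placed to supply. PANESS, TMS, MRI/MRS, ADHD-RS, BRIEF-2 and TOVA are all repeated at Week 12.

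The second is adherence at Visit 3. The day-count floors exist so that the end-of-treatment ratings reflect treatment. Because the section joins counts and log review with *and/or*, the floors may be checked at Visit 3 from the family's own log alone. A first count at Week 12 could not, by itself, separate doses taken before Week 8 from doses taken after it.

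**Working it through.** The plan gives no figure for leftover drug. The one figure beside the return condition, total payment, reproduces: 3 × $25 + $100 = $175.

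**Inputs from the documents**
- Supply period: 8 weeks = 56 days (Cost of Participation).
- Dosing: twice daily (Table 3), so 56 × 2 = 112 doses.
- Floors: 4 of 7 days in general, 5 of 7 in each of the last two weeks (Compliance and Safety Monitoring).
- Washout: Week 8 to Week 12 = 28 days (Table 4).

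**Assumptions, because the documents are silent**
- Exactly 56 days of drug are dispensed, with no overage.
- A day on treatment means both doses were taken.
- Missed doses remain in the home.

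**Formula:** leftover days at Week 8 = 56 − days on treatment.

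**Dosing over a full 56 days**
- Full adherence: 56 − 56 = 0 days.
- 5 of 7 days throughout: 56 − 8 × 5 = 16 days; 16/28 = 57% of the washout.
- At the floors: days taken = 6 × 4 + 2 × 5 = 34; leftover = 56 − 34 = 22 days (44 doses); 22/28 = 79%.

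**Dosing from Week 1 to Week 8, as Table 4 is labelled (49 days)**
- Full adherence: 56 − 49 = 7 days (14 doses); 7/28 = 25%.
- At the floors: days taken = 5 × 4 + 2 × 5 = 30; leftover = 56 − 30 = 26 days (52 doses); 26/28 = 93%.

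Overage would add to all of these figures. So would an interruption or reduction under the dose modification guidelines if the drug already dispensed stays with the family.

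**A related conflict.** The adherence paragraph asks for full compliance over the two days before the last study visit and its TMS session. In Table 4 the last visit is Week 12, when treatment has been stopped for four weeks. The two cannot both be followed as written and must be reconciled.

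**The case against.** The return condition sits in a payment paragraph, which explains why one visit pays more. It is not a drug-accountability procedure. A reader might infer that drug comes back at Visit 4 and at no other time, but the text does not say so, and it does not bar a count or collection at Visit 3. This stands: the point is that Visit 4 is the only timing stated, not that the plan rules out others.

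A reader might also infer that adherence at Visit 3 goes unchecked. The documents do not support that. A medication log is scheduled at Week 8, counts are provided for, and missed doses are queried. The floors are conditions for obtaining a rating, and a count requires only that the drug be brought in. What remains is narrower: no count is assigned to Visit 3, and log review alone would satisfy the text. The diary is the weaker part of the point, because the documents do not say whether it and the medication log are the same record.

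The logs at Weeks 8, 10 and 12 bracket the washout, so a Week 12 count would not be the sole source. They can mitigate the problem but, where they rest on family report, not remove it.

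Applying 4 of 7 days to all eight weeks would give 24 leftover days, or 86% of the washout. That breaks the higher floor for the last two weeks, so 22 days is the figure for a full 56 days of dosing. The lower end is 0.

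Finally, the protocol notes that NAC can be bought over the counter. Collecting study drug does not by itself guarantee an NAC-free washout.

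**Conclusion.** The point holds as a missing control. The only stated time for returning unused drug falls after the off-drug interval, and Table 4 assigns neither a return nor an objective count to the visit that ends treatment. A child who meets the plan's own adherence floors could hold 22 days of drug at Week 8 if dosing covers 56 days, or 26 days if it covers 49. A fully adherent child would hold 0 or 7. These figures rest on exactly 56 days being dispensed and on reading a treatment day as both doses.

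A reader might go further and conclude that persistence of effect will be overstated at Week 12. The documents do not show this. The figures measure drug held, and nothing indicates that children who missed doses during treatment would take them afterwards.

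The reach is also limited. The sample size and the 20% improvement criterion rest on change to Week 8, and the listed correlations use two-month change. The primary comparison, power and alpha do not move. What is at stake is the Week 12 washout reading and objective support for adherence at Visit 3.

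**What to change.** 1. In the compensation section, move the return of the diary and all unused study drug from Visit 4 to Visit 3.
2. In Table 4, add a drug-return and count row at Visit 3. In the Compliance and Safety Monitoring section, name that visit for the count.
3. Use the medication logs already scheduled at Weeks 10 and 12 to record any study drug or over-the-counter NAC taken since Visit 3.
4. In the same edit, reconcile the full-compliance requirement before the last study visit with Table 4, where that visit is off drug.

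The cost is a few sentences and one table row. Visit 3 is already on site, so no visit or procedure is added beyond taking in and counting the drug. Moving the payment along with the return would weaken the incentive to attend Visit 4. Leaving the $100 at Visit 4 and moving only the return condition avoids that.
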